5.5.2. Other Comparisons of Interest

If the primary comparison of interest (Section 5.5.1) using the ITT-E population demonstrates non-inferiority of Q8W compared to Q4W then the following key secondary comparisons will be tested:

- Treatment with Q8W will be declared non-inferior to Q4W with respect to the proportion of participants with HIV-1 RNA < 50 c/mL at Week 48 (defined by the US FDA snapshot algorithm) if the lower end of a two-sided 95% confidence interval for the difference between in rates (Q8W – Q4W) lies above -10% using the ITT-E population
- Superiority of Q8W compared to Q4W with respect to change from baseline HIVTSQs total score at Week 48 using the ITT-E population and a two-sided 5% level of significance. Refer to Section 12.5.1 for details.

For the primary endpoint treatment comparison at Week 48, no multiple comparison adjustment is necessary for testing non-inferiority followed by superiority (conditional on achieving a significant test for non-inferiority) since testing follows a pre-specified sequence of hypothesis such that if the first hypothesis tested is not significant, all subsequent tests will not be performed. This fixed sequence procedure controls the type I error rate at the nominal level. The primary endpoint treatment comparison at Week 48 will also be performed using the PP population and the results will be compared for consistency with the results from the ITT-E population.

In addition to the primary and the key secondary comparisons, the comparisons between two treatment arms for ACCEPT (general acceptance score), PIN (Domain scores (CCI [REDACTED] and CCI [REDACTED]) and Individual Items Scores (CCI [REDACTED])), HAT-QoL (Life satisfaction, HIV medications, disclosure worries) and HIVTSQc (Treatment Satisfaction score) at timepoints through Week 48 will also be performed as supportive analyses.

Lastly, for the IDMC interim analyses, since the statistical stopping guidelines will not result in early stopping for positive efficacy findings, these interim treatment comparisons will not inflate the Type I error rate for the primary treatment comparison.

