2.3. Study Design

Overview of Study Design and Key Features	

The diagram illustrates the study design timeline. It is divided into three phases: Screening Phase, Maintenance Phase, and Extension Phase. The Screening Phase starts at Day 1 and includes randomization (1:1) for two arms: the ATLAS Q4W Arm and the ATLAS SOC Arm + additional SOC Patients. The Maintenance Phase (from Day 1 to Week 100) involves randomization (1:1) into Q4W CAB LA + RPV LA and Q8W CAB LA + RPV LA regimens. The Extension Phase (starting at Week 100) involves CAB LA + RPV LA Q4W or Q8W. Key events include the 1° Endpoint at Week 48 and the 2° Endpoint at Week 100.
	

N=1020, randomized 1:1 to each arm and stratified by prior CAB+RPV Exposure
 
# SOC Patients not transitioning from the ATLAS study must be on uninterrupted current regimen (either the initial or second cART regimen) for at least 6 months prior to Screening. Documented evidence of at least two plasma HIV-1 RNA measurements <50 c/mL in the 12 months prior to Screening: one within the 6 to 12 month window, and one within 6 months prior to Screening. No history of virologic failure. No evidence of viral resistance based on the presence of any resistance-associated major INI, or NNRTI mutation (except K103N) from prior genotype assay results. No current or prior history of etravirine use.
 
†Optional Extension Phase to continue randomized CAB LA + RPV LA Q4W or Q8W at Wk 100
 
‡Participants who withdraw from IM arm must go into 52 week long term follow up phase if randomized regimen is not yet locally approved and commercially available.
	

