5.5. Multiple Comparisons and Multiplicity

5.5.1. Primary Comparison of Interest

The primary analysis will be based on the ITT-E population. The primary comparison will be made at a one-sided 2.5% level of significance. Treatment with Q8W will be declared non-inferior to Q4W if the upper end of a two-sided 95% confidence interval for the difference between the two groups (Q8W – Q4W) in the proportion of participants with HIV-1 RNA ≥50 c/mL at Week 48 (defined by the US FDA snapshot algorithm) lies below 4%.

The primary comparison of interest is the comparison between Q8W (CAB LA + RPV LA Q8W) and Q4W (CAB LA + RPV LA Q4W) for the primary endpoint in the ITT-E population. This analysis will be adjusted for by the re-derived randomization strata based on eCRF data.

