$$P_k = \frac{n_k^2 y_k - m_k^2 x_k + n_k m_k (m_k - n_k) / 2}{N_k^2}$$

$$Q_k = \frac{x_k (m_k - y_k) / N_k + y_k (n_k - x_k) / N_k}{2}$$

with x_k and y_k corresponding to the number of participants with Plasma HIV-1 RNA ≥ 50 c/mL at Week 48 per FDA Snapshot for Q8W and Q4W, respectively, for the k th stratum.

Model Results Presentation

- Adjusted CMH estimate of the difference in the proportion of subjects with Plasma HIV-1 ≥ 50 c/mL between each treatment group (Q8W – Q4W) and corresponding 95% confidence interval.
- Non-inferiority will be concluded if the upper bound of the two-sided 95% confidence interval for the CMH adjusted treatment difference (Q8W – Q4W) is less than 4%.
- If this analysis shows non-inferiority, then a superiority hypothesis will be tested at the two-sided 5% level of significance. Superiority favoring Q8W will be declared if the upper bound of the confidence interval is below 0% for the ITT-E population analysis. If superiority is declared, the p-value for superiority will also be calculated.

Subgroup Analyses

1. Treatment Heterogeneity across rederived randomization strata [prior exposure to CAB+RPV (0 weeks, 1-24 weeks, >24 weeks)]:
 - The weighted least squares chi-squared statistic [Fleiss, 1981] will be used to test for one-way homogeneity across the levels of each categorical variable, with each categorical variable considered separately.
 - Following Lui and Kelly [Lui, 2000] $\frac{1}{2}$ will be added to each cell in any strata for which the stratum-specific rate estimates of either f_{Q8W} or f_{Q4W} are zero or one, and tests will be one-sided.
 - Any heterogeneity found to be statistically significant will be explored and if necessary results will be reported for each level of the categorical variable. Investigation of heterogeneity will be confined to the primary endpoint. Tests of homogeneity will be assessed at the one-sided 10% level of significance.
2. Stratum-specific analyses for two groups of participants: (Group 1) those currently receiving Standard of Care antiretroviral therapy at Baseline (i.e. no prior exposure to CAB+RPV), (Group 2) those receiving Q4W CAB LA + RPV LA therapy in the ongoing ATLAS study (i.e. have prior exposure to CAB+RPV). For each stratum (Group 1 and Group 2), the following will be presented:
 - Proportion of subjects with plasma HIV-1 RNA ≥ 50 c/mL at Week 48 by treatment group.

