
 • The analysis for HIVTSQs, ACCEPT and HAT-QoL will be performed for subjects with and without prior exposure to CAB+RPV separately. 
 ○ For subjects without prior exposure to CAB+RPV, an analysis of covariance (ANCOVA) model will be used at each visit during the maintenance phase with covariates: treatment, age (<50, ≥ 50 years old), sex at birth, race (i.e. white, non-white) and baseline score value for other endpoints (as a continuous variable). ○ For subjects with prior exposure to CAB+RPV, an analysis of covariance (ANCOVA) model will be used at each visit during the maintenance phase with covariates: treatment, age (<50, ≥ 50 years old), prior exposure to CAB+RPV (i.e. 1 to 24 weeks, >24 weeks), sex at birth, race (i.e. white, non-white) and baseline score value (as a continuous variable). • For PIN, an analysis of covariance (ANCOVA) model will be used at each visit during the maintenance phase with covariates: treatment, age (<50, ≥ 50 years old), prior exposure to CAB+RPV (i.e. 0 weeks, 1 to 24 weeks, >24 weeks), sex at birth, race (i.e. white, non-white), and Week 8 score value (as a continuous variable). • Adjusted point estimates will be derived as LSMEANS using the observed margins (OM) option within PROC MIXED in SAS. • The superiority testing of Q8W compared to Q4W with respect to change from baseline in HIVTSQs total score at Week 48 will be performed using the fixed sequence procedure to control for the type I error rate at the nominal level of 5%. If the superiority testing within subjects without prior exposure to CAB+RPV demonstrates Q8W is superior to Q4W in change from baseline in HIVTSQs total score at Week 48 at two-sided 5% level of significance, the superiority testing at the same level of significance (i.e. two-sided 5%) within subjects with prior exposure to CAB+RPV will be followed. No adjustment for multiplicity will be applied for other tests as they will be considered supportive. • Interactions between treatment and each of the covariates will not be assessed unless the exploratory subgroup analyses on the primary endpoint highlights significant interactions. In this situation, the interaction(s) of interest will be assessed and, if necessary, results will be reported in the clinical study report. Interactions between treatment and the baseline score will be investigated but not included in the model. If interactions are found to be significant ($p < 0.10$), results may be presented separately by subgroup.

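### After primary non-inferiority, three further claims are each tested at the full level with no order or alpha split between them

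*SAP*

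**What the plan says.** **Primary test.** Section 5.5.1: "The primary comparison will be made at a one-sided 2.5% level of significance". Section 7.1.5.1 gives the decision rule: "Non-inferiority will be concluded if the upper bound of the two-sided 95% confidence interval for the CMH adjusted treatment difference" is below 4%.

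**Key secondaries.** Section 5.5.2: if the primary comparison in ITT-E "demonstrates non-inferiority of Q8W compared to Q4W then the following key secondary comparisons will be tested". Two unnumbered bullets follow. The first is non-inferiority on <50 c/mL at Week 48, judged by a two-sided 95% confidence interval against -10%. The second is "Superiority of Q8W compared to Q4W with respect to change from baseline HIVTSQs total score at Week 48 using the ITT-E population", at two-sided 5%, with a pointer to Section 12.5.1. Section 7.2.5.1 repeats the <50 c/mL rule and does not tie it to the other tests.

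**Primary superiority.** Section 7.1.5.1: "If this analysis shows non-inferiority, then a superiority hypothesis will be tested at the two-sided 5% level of significance". The claim for Q8W needs the upper confidence bound to be below 0%.

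**Statements of error control.** There are two.
- Section 5.5.2: "This fixed sequence procedure controls the type I error rate at the nominal level". This closes a paragraph about the primary endpoint only, non-inferiority and then superiority.
- Section 12.5.1 orders the HIVTSQs tests: "If the superiority testing within subjects without prior exposure to CAB+RPV demonstrates Q8W is superior to Q4W" at two-sided 5%, the same test follows in participants with prior exposure. Other tests there are called supportive and left unadjusted.

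**The concern.** A fixed sequence controls error because a failure stops everything after it. Here success on the primary opens three branches side by side. A failure on <50 c/mL does not stop HIVTSQs, and a failure on HIVTSQs does not stop superiority on >=50 c/mL. Each branch spends the full alpha again.

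The SAP treats these tests as more than descriptive. It separates the key secondaries from the supportive analyses, and it sequences HIVTSQs expressly to control type I error. At stake is how a superiority or key secondary claim in the study report may be described. As written, the plan does not support presenting these claims together as controlled at the nominal level.

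A smaller point sits alongside. The HIVTSQs bullet in Section 5.5.2 reads as one test in ITT-E, whereas Section 12.5.1 runs two tests, by prior exposure.

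**Working it through.** **Inputs from the SAP.** One-sided 2.5% for the primary (5.5.1). Superiority on >=50 c/mL at two-sided 5%, which is 2.5% in favour of Q8W (7.1.5.1). Non-inferiority on <50 c/mL by a 95% interval, which is one-sided 2.5% (5.5.2). HIVTSQs superiority at two-sided 5%, which is 2.5% in favour of Q8W (5.5.2, 12.5.1). Sample size: "N=1020, randomized 1:1 to each arm and stratified by prior CAB+RPV Exposure" (2.3), so 1020/2 = 510 per arm.

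**Step 1: the SAP's own statement.** Primary non-inferiority followed by primary superiority is a true fixed sequence, so alpha is spent once: 2.5%. The statement is reproduced. The HIVTSQs order (without, then with, prior exposure) also adds nothing to its own 2.5%.

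**Step 2: realistic case.** Suppose primary non-inferiority and <50 c/mL non-inferiority are both truly met, and the arms are equal on >=50 c/mL and on HIVTSQs. Two false claims remain possible. With independence:

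1 - (1 - 0.025)^2 = 1 - 0.9506 = 0.0494, or 4.9%.

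Without assuming independence, the upper bound is 0.025 + 0.025 = 5.0%.

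**Step 3: worst case.** With all three later nulls true, each at its boundary, and independent:

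1 - (1 - 0.025)^3 = 1 - 0.9269 = 0.0731, or 7.3%; upper bound 3 x 0.025 = 7.5%.

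The Snapshot categories in Section 15.9 (<50, >=50, no virologic data) sum to 100%, so the three arm differences sum to zero. A <50 c/mL difference of -10 points with a >=50 c/mL difference of 0 forces +10 points of no virologic data on Q8W.

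**Step 4: check by simulation.** 1,000,000 trials, 510 per arm, unadjusted Wald intervals. The SAP states no rates, so these are assumptions: >=50 c/mL 1% to 4% in both arms; <50 c/mL 94% vs 94%, or 94% (Q4W) vs 84% (Q8W); HIVTSQs independent of virology.

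| Case | Formula | Simulated |
|---|---|---|
| Primary superiority and HIVTSQs | 4.9% | 4.6% to 4.9% |
| All three | 7.3% | 6.7% to 7.2% |
| One fixed sequence over all tests | 2.5% | 2.3% to 2.7% |

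The excess over 2.5% in the last row comes from the Wald interval at the -10% margin, not from multiplicity. The primary passes with probability 0.90 to 1.00 under these rates, so requiring it first protects the later claims very little.

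**The case against.** **No control sentence is false.** This stands. Each covers only its own pair, and each is right for that pair. What is missing is the link between the branches.

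**The primary conclusion is untouched.** This also stands: it remains at one-sided 2.5%, so the point is not a threat to the trial's main result.

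**4.9% is within a 5% level.** That compares unlike quantities. The 4.9% counts errors in favour of Q8W only, for which the level is 2.5%. Counting both directions for the two superiority tests gives 1 - 0.95^2 = 9.75% against 5%.

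**The bullets may be meant as an order.** The SAP does not say so. Even on that reading, superiority on >=50 c/mL runs in parallel, and step 2 still applies.

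**The 7.3% is an extreme corner.** This stands. It needs independence between categories of one classification and the 10-point excess of missing data shown above. It should not be read as the expected error rate.

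**HIVTSQs.** A reader might infer that it is undefined which HIVTSQs result carries the claim, or that a pooled ITT-E test could be chosen instead of the stratum tests. The document does not support that. The bullet refers to Section 12.5.1, which fixes two tests and their order. Tables 6.21 and 6.22 (Section 15.14.5.10) present exactly those two, both listed under ITT-E. No pooled HIVTSQs model is specified, so there is no rival result. What is left is a summary bullet worded as a single test.

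**Conclusion.** The point holds in this form: the three claims that follow primary non-inferiority are each tested at the full level, and the SAP gives no rule across them, so their joint error rate is not controlled. The realistic size is up to 4.9% against one-sided 2.5%, about double. This assumes that <50 c/mL non-inferiority is truly met, that the arms are equal on the other two endpoints, and that those two tests are independent. The 7.3% figure is a ceiling under implausible conditions.

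A reader might go further and infer that the SAP's statements of control are wrong or that the primary analysis is inflated. Neither follows. This should be fixed, but it does not put the primary result in doubt.

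**What to change.** Before the Week 48 unblinding described in Section 3.2, amend Section 5.5.2 to state one hierarchy that covers <50 c/mL non-inferiority, the two HIVTSQs stratum tests and superiority on >=50 c/mL, stopping at the first failure. The order is for the sponsor to choose; several are valid. Alternatively, split alpha: Bonferroni over the three claims gives 0.025/3 = 0.0083 one-sided each, and Holm starts at the same value. Repeat the chosen rule in Sections 7.1.5.1, 7.2.5.1 and 12.5.1.

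Reword the HIVTSQs bullet in Section 5.5.2 to name the two sequential tests of Section 12.5.1.

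The cost is SAP wording, with no change to data collection or models. With a hierarchy, an early failure blocks the tests after it. With a split, each test has a smaller alpha and so less power. An order chosen after the results are known would not be credible.

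### Section 5.5.2 declares one HIVTSQs superiority hypothesis in ITT-E, Section 12.5.1 tests two ordered exposure subsets, and nothing says what may be claimed if only the first succeeds

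*SAP*

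**What the plan says.** Section 5.5.2 makes the key secondary comparisons conditional on the primary result. If the primary analysis "demonstrates non-inferiority of Q8W compared to Q4W then the following key secondary comparisons will be tested". One of them is "Superiority of Q8W compared to Q4W with respect to change from baseline HIVTSQs total score at Week 48 using the ITT-E population", at two-sided 5%.

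Section 12.5.1 sets out the models: "The analysis for HIVTSQs, ACCEPT and HAT-QoL will be performed for subjects with and without prior exposure to CAB+RPV separately". The confirmatory tests follow a fixed sequence. The first condition is "If the superiority testing within subjects without prior exposure to CAB+RPV demonstrates Q8W is superior to Q4W" at two-sided 5%; if it is met, "the superiority testing at the same level of significance (i.e. two-sided 5%) within subjects with prior exposure to CAB+RPV will be followed".

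The display list matches Section 12.5.1. Table 6.21 and Figures 6.1 and 6.3 cover participants without prior exposure; Table 6.22 and Figures 6.2 and 6.4 cover those with it. The pooled displays of the total score, Tables 6.16 and 6.17, are descriptive.

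The two models word the baseline covariate differently. The list for participants without prior exposure ends with "baseline score value for other endpoints (as a continuous variable"). The list for participants with prior exposure names the baseline score with no qualifier.

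**The concern.** A key secondary claim should match the test that carries it. Here the claim concerns the whole ITT-E population, while the tests concern two parts of it in order. Section 12.5.1 does not say which result, or combination of results, permits the ITT-E statement. If only the first test succeeds, the study report could declare superiority in ITT-E on evidence from participants without prior exposure alone, after the test in the remaining participants had failed.

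The baseline qualifier matters because it sits in the model for the first test, which decides whether the second is performed. Read literally, it leaves open whether baseline HIVTSQs is a covariate there.

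**Working it through.** **Type I error.** The only HIVTSQs figure that can be reproduced is the nominal 5%. In a fixed sequence, a false rejection requires rejection of the first true null in the order, so the family-wise error is at most 0.05. A simulation of 2,000,000 draws with both nulls true gave 0.0499. Without the order it would be 1 − 0.95² = 0.0975. The stated 5% therefore holds for the two subset hypotheses.

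**What each outcome supports.** The subsets are disjoint and together make up ITT-E.

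| First test (no prior exposure) | Second test (prior exposure) | What the tests support | What the SAP says about the ITT-E claim |
|---|---|---|---|
| Succeeds | Succeeds | Superiority in both parts, hence across ITT-E | Nothing explicit |
| Succeeds | Fails | Superiority without prior exposure only | Nothing |
| Fails | Not performed | No confirmatory claim | Nothing explicit |

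The second row is the gap.

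**How likely is the second row?** The SAP gives N = 1020 randomised 1:1, about 510 per arm. It gives no SD, effect size, power or subset sizes for HIVTSQs. Assume a standardised effect d equal in both subsets and a share f without prior exposure. The power of a subset test with n per arm is Φ(d√(n/2) − 1.96), with n = 510f for the first test and 510(1 − f) for the second. The probability that only the first succeeds is p1 × (1 − p2). For d = 0.20:

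- f = 0.5: p1 = 0.617, p2 = 0.617; 0.617 × 0.383 = 0.236
- f = 0.6: p1 = 0.696, p2 = 0.524; 0.696 × 0.476 = 0.331
- f = 0.7: p1 = 0.762, p2 = 0.417; 0.762 × 0.583 = 0.444

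For d from 0.15 to 0.25 and the same shares, the range is 0.16 (0.806 × 0.194, at d = 0.25 and f = 0.5) to 0.44.

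**Are the hypotheses interchangeable?** Two assumed patterns, with f from 0.5 to 0.7, show that they are not.

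- Effect 0 without prior exposure and 0.4 with it: the pooled effect is 0.4(1 − f), that is 0.20 to 0.12. A pooled test of 510 per arm has power 0.89 to 0.48, whereas the first subset test rejects only 5% of the time.
- Effect 0.3 without prior exposure and an opposite effect with it that cancels overall: the pooled difference is zero, yet the first subset test rejects with probability 0.92 to 0.98.

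**Baseline covariate.** If baseline were omitted from the first model, and variances at baseline and Week 48 were equal, the ratio of the ANCOVA SE to the change-score SE would be √((1 + ρ)/2). For ρ = 0.5 this is 0.866, so omission raises the SE by 1/0.866 − 1 = 15%. For ρ = 0.2 it is 0.775, giving 29%. The correlations are assumed, and the SAP does not show that omission is planned.

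**The case against.** The strongest reply is that Section 5.5.2 is a summary that hands over to the detailed section: "using the ITT-E population and a two-sided 5% level of significance. Refer to Section 12.5.1 for details". On that reading ITT-E names the analysis set, and Section 12.5.1 gives the operational rule. Tables 6.21 and 6.22 both list ITT-E as their population.

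The split also looks deliberate. Section 5.4.2 assigns the 0 versus ≥1 week grouping to the health outcomes analyses, and the HIVTSQs, ACCEPT and HAT-QoL change-from-baseline displays follow it. There is a good reason for it: one group's baseline score rates oral therapy and the other's rates Q4W injections, so change from baseline means different things. The pooled PIN model is a weak counterexample, because PIN change is measured from Week 8, when all participants are scheduled to be on injections.

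Most of this stands. A reader might infer that no analysis supports the ITT-E claim at all. The documents do not support that, since success in both ordered tests covers all of ITT-E with alpha held at 5%. A reader might also infer that the plan loses power by starting in a subset. There is no planned HIVTSQs power figure to fall short of, and any comparison with a pooled test rests on assumed shares and a common effect that the split design does not presuppose. That a failed first test ends testing is a property of every fixed sequence.

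The reply does not say what may be claimed when only the first test succeeds. A cross-reference can supply a model, but it cannot settle that silently.

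**Conclusion.** The mismatch is real but limited. Section 5.5.2 states one hypothesis in ITT-E, Section 12.5.1 tests two ordered subset hypotheses, and no rule links them. As written, success in the first test alone leaves room for an ITT-E superiority statement that no test supports. Under a standardised effect of 0.20 in both subsets and 50-70% of participants without prior exposure, that outcome has probability 0.24-0.44. These inputs are assumptions, and the figure is not a shortfall against anything in the SAP. The primary analysis and error control within the sequence are unaffected.

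On the baseline covariate, a reader might infer that baseline HIVTSQs is left out of the first model. The text does not establish this. The qualifier names no excepted endpoint, and the same section plans to examine treatment-by-baseline-score interactions, and to footnote them, without excepting HIVTSQs. It is an ambiguity, probably leftover text, in the model where it matters most.

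**What to change.** In Section 5.5.2, replace the single HIVTSQs bullet with two ordered hypotheses: superiority at Week 48 in participants without prior CAB+RPV exposure and then, only if that succeeds, in participants with prior exposure, each at two-sided 5%. State that success in the first alone supports a claim only for participants without prior exposure, and that a claim across ITT-E requires both.

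A pooled ITT-E ANCOVA adjusted for exposure stratum and baseline score may be added as supportive. It should become the confirmatory test only if the sponsor truly intends a single ITT-E claim. That would be a choice of estimand, with the drawback that it averages over participants coming from oral therapy and from Q4W injections.

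In Section 12.5.1, delete the words *for other endpoints* from the no-prior-exposure model, so that baseline HIVTSQs is plainly a covariate in both models.

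The cost is a few sentences of SAP text, plus one extra model if the pooled analysis is added. The change should be made before unblinding.
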